10.1.3. Measurement Methods

Degree of healing will be based on visual assessment by the surgeon with the following metrics on a visual analog scale (VAS): vascularization, overall healing (0-100%). Photographs will be taken, stored and transmitted securely to BOX. Time to complete healing will be defined as the first visit at which the surgeon determine that there is >99% overall healing of the graft.

10.1.4. Measurement Time Points

Healing assessment will take place at each postoperative visit until healed including day 7, 14, 28, and 42. Further early postop follow up visits may be considered as determined by the surgeon.

10.1.5. Response Review

N/A

10.2. Primary outcome measure: device safety

10.2.1. Relevant Subset

All patients (n=15).

10.2.2. Measurement Definition

Safety of the device will be measured by any observed complications that occur following treatment. Primary safety endpoints will include presence/absence of infection, necrosis, allergic reaction, or any complication that can be attributed to the graft procedure. The degree and frequency of these adverse events will be recorded and reported. These endpoints will be reported in the study case report form (CRF) and will be continuously tabulated and reviewed by the study staff.

10.2.3. Measurement Methods

Photographs will be taken using standardized digital photography, stored and transmitted securely to surgeon for independent review. Grafts will be evaluated by the surgeon with the following metrics on a visual analog scale (VAS): ischemia/necrosis (0-100%); dehiscence (0-100%). In evaluating for complications, the surgeon will classify grafts as having A) no infection; B) hyperemia (no infection); C) cellulitis (superficial infection); D) abscess or purulent infection. Additional adverse events or complications (as defined in CTCAE v4.03, see **Section 7.2**) will also be recorded and reported in categorical format.

10.2.4. Measurement Time Points

Healing assessment will take place at each postoperative visit until healed including day 7, 14, 28, and 42. Further early postop follow up visits may be considered as determined by the surgeon.

10.2.5. Response Review

N/A

10.3. Secondary outcome measure: Time to 50% and 75% graft healing

10.3.1. Relevant Subset

All patients (n=15).

10.3.2. Measurement Definition

Time to 50% and 75% healing for each NACgraft™ will be as the first weekly visit at which the surgeon deems the graft >50% healed and >75% healed, respectively. This measurement will be reported as the number of weeks to healing.

10.3.3. Measurement Methods

See Section 10.1.3.

10.3.4. Measurement Time Points

See Section 10.1.4.

10.3.5. Response Review

See Section 10.1.5.

10.4. Secondary outcome measure: operative time

10.4.1. Relevant Subset

All patients (n=15).

10.4.2. Measurement Definition

Operative time will be defined as the amount of time passing between incision of the skin and final suture placement during graft surgery.

10.4.3. Measurement Methods

Operative time will be measured in the procedure room with a standard stopwatch and reported in minutes/seconds. If in the operating room this is reported by operating staff. If done in the clinic, the procedural nurse will assist with timekeeping. Operative time will be recorded separately for each NACgraft™ during bilateral procedures.

10.4.4. Measurement Time Points

Measurements will take place on day 0 (day of surgery)

10.4.5. Response Review

N/A

10.5. Secondary outcome measure: NAC sensitivity10.5.1. Relevant Subset

All patients (n=15).

10.5.2. Measurement Definition

NAC sensitivity is defined as the sensation felt by the patient on the NACgraft™ according to the scale in **Section 10.5.3.**

10.5.3. Measurement Methods

Measurement is performed using Semmes Weinstein Monofilament (SWM) testing with the patient lying down with her eyes closed. The areola will be divided into quadrants, so a total of 5 regions (nipple + each areolar quadrant) will be assessed. Each monofilament represents a log of the force needed to bend the microfilament, with the larger monofilaments requiring more force to bend. Filament sizes will be converted to categorical variables (0 = no sensation, i.e. unable to feel 6.65 filament; 1 = can feel 6.65 filament, 2 = can feel 4.56 filament, 3 = can feel 4.31 filament, 4 = can feel 3.61 filament, and 5 = can feel 2.83 filament).

10.5.4. Measurement Time Points

Measurements will take at 3 months, 6 months, and 12 months.

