NAC Sensitivity	X					X	X	X	Surgeon		Sensitivity testing will be performed with the patient laying down and eyes closed. The areola will be divided into 4 quadrants, plus the nipple, for a total of 5 regions to be tested using the Semmes Weinstein monofilament technique.
Patient Surveys	X					X	X	X	Study Site Staff		Patients will complete the Nipple Reconstruction Satisfaction Survey – Pre at Screening and Nipple Reconstruction Satisfaction Survey – Post at Days 90, 180, and 360.

a: window +/- 4 days| b: subject discretion and/or PI discretion to continue beyond 6 weeks

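### The calendar schedules a Screening sensitivity test that section 10.5 does not define and section 12.5.2 does not use, so a post-operative score alone does not show whether sensation was gained

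*Combined protocol and SAP*

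**What the plan says.** The calendar row in section 9 reads "NAC Sensitivity X X X X Surgeon", with the first mark in the Screening column. The row's text adds only how the test is done: "Sensitivity testing will be performed with the patient laying down and eyes closed", in five regions.

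The measurement section differs. Section 10.5.2 states: "NAC sensitivity is defined as the sensation felt by the patient on the NACgraft™". Section 10.5.3 divides the site, "so a total of 5 regions (nipple + each areolar quadrant) will be assessed", and says "Filament sizes will be converted to categorical variables", scored 0 (largest filament not felt) to 5 (finest filament felt). Section 10.5.4 gives the time points: "Measurements will take at 3 months, 6 months, and 12 months". The synopsis and section 4 also place sensitivity testing at Days 90, 180 and 360.

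Section 12.5.2 takes the secondary outcomes as sections 10.3 to 10.9 describe them. It summarises each, sensitivity included, by mean, median, maximum and a 95% confidence interval. It names no baseline value and no change score for sensitivity.

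**The concern.** Sensation is a stated secondary objective, and section 2.2 expects neural elements to repopulate the device. The natural question at 12 months is therefore whether sensation was gained at the site. A post-operative score alone does not answer it, because the reconstructed mound may already have had sensation. The protocol allows for this: the pre-operative survey in Appendix B asks about pleasant and unpleasant sensation in each breast. Those answers are self-reported on a coarse four-level scale and cannot be subtracted from a monofilament score. Entry is open from 3 months after reconstruction with no upper limit (section 3.1.2), so starting levels may vary between patients.

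There is also a practical problem. A site that follows the calendar will collect a Screening score that no text defines or analyses. A site that follows 10.5.4 will collect none. Section 12.1 promises to assess missing measurements for each outcome, which is hard to do while the documents disagree on whether a measurement is due.

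**Working it through.** **1. Is the calendar mark really at Screening?** The calendar has nine visit columns (Screening, then Days 0, 7, 14, 28, 42, 90, 180 and 360). In the table text available to me, the sensitivity row has only eight visit cells, with marks in cells 1, 6, 7 and 8. One blank cell has been lost, so counting columns is unsafe for the later marks. The Patient Surveys row has marks in the same cells, and its text gives the visits in words: "Pre at Screening and Nipple Reconstruction Satisfaction Survey – Post at Days 90, 180, and 360". The shared pattern therefore means Screening plus Days 90, 180 and 360. The engraftment row, marked in cell 2 for Day 0, confirms that cell 1 is Screening.

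**2. The sources side by side.**

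| Source | Screening | Days 90, 180, 360 |
|---|---|---|
| Calendar, section 9 | yes | yes |
| Section 10.5.4 | no | yes (3, 6, 12 months) |
| Synopsis and section 4 | not mentioned | yes |
| Section 10.5.2 | no defined target before engraftment | sensation on the graft |
| Section 12.5.2 | no change score | summary of each outcome |

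Other endpoints do name their reference point: enrollment for satisfaction (10.8.4), and day 0 for projection and diameter (10.6.4, 10.7.4).

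**3. What a post-operative score leaves open.** Change = post-operative score minus Screening score, each from 0 to 5. For a 12-month score of 2, Screening scores of 0, 1, 2, 3, 4 and 5 give changes of +2, +1, 0, -1, -2 and -3. The planned summary reports 2 in every case.

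**4. Precision.** The documents give no standard deviation (SD), correlation or target width for this endpoint, so there is no stated figure to reproduce. For illustration, assume one value per patient, n = 15, equal SDs at both visits and no missing data.

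- Single-visit mean, as planned: half-width = t(0.975, 14)/√15 × SD = 0.554 SD.
- Mean change from Screening: half-width = 0.554 × √(2(1 − r)) × SD, where r is the assumed within-patient correlation.

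| r | 0 | 0.3 | 0.5 | 0.7 | 0.9 |
|---|---|---|---|---|---|
| Half-width, SD units | 0.78 | 0.66 | 0.55 | 0.43 | 0.25 |

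The change is estimated more precisely than the single-visit mean only when r exceeds 0.5. The reason to use the baseline is that it answers a different question.

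**5. Unit of analysis.** Bilateral grafting is allowed, so 15 patients supply between 15 and 30 breasts, each tested in five regions. Two breasts of one patient are not independent, and any interval must reflect that.

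**The case against.** The strongest reply is that the calendar mark is stray. The endpoint definition, the time points, section 4 and the synopsis agree with one another, and one calendar cell differs. A test of sensation on the graft cannot be done before the graft exists, and nipple and areolar quadrants have no referent on a mound without a NAC. This explanation is live, and it is why the fix offers two routes. It does not remove the contradiction or the limit on what a post-operative score can show.

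It is also fair to say that the objective is sensation up to 12 months and claims no gain. The endpoint is descriptive, section 12.6.2 disclaims definitive conclusions even for the primary measures, and sensitivity testing is not a separate criterion for proceeding in section 12.7. All of that stands and bears on severity.

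A reader might infer three stronger things that the documents do not support.

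- **That pre-existing and graft sensation cannot be separated at all.** If sites follow the calendar, Screening scores will exist and a change can be computed. Section 12.5.2 does not limit itself to post-operative scores, and the synopsis promises summaries at each time point. The gap is that no text defines the test or plans the comparison.
- **That pairing narrows the interval by 26% to 43%.** Those figures set the paired half-widths (0.554 and 0.429 SD) against a two-independent-group comparison, t(0.975, 28) × √(2/15) = 0.748 SD. This single-arm plan makes no such comparison. Its single-visit mean already has half-width 0.554 SD.
- **That within-patient change is the only control available.** Section 12.6.3 plans comparison with historical figures, although none of those listed concerns sensation.

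**Conclusion.** The inconsistency is real: the calendar schedules a Screening sensitivity test that 10.5.4 omits, 10.5.2 gives no target for, and 12.5.2 does not use. On the plan as written, a post-operative score does not distinguish sensation gained from sensation already in the mound. A score of 2 leaves a six-value range of possible change, from -3 to +2.

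The severity is minor. Only the interpretation of a descriptive secondary endpoint is affected, and no gain in precision is claimed. The conclusion rests on reading the first mark in the sensitivity row as Screening, which the matching survey row and its text support. A Screening score would reduce the ambiguity but not remove it, since pressure applied to the graft may be felt by the tissue beneath.

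**What to change.** If Screening testing is intended:

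- **10.5.4:** add Screening to the time points, to agree with the calendar.
- **10.5.2 and 10.5.3:** define the Screening test as monofilament testing at the planned recipient site, in the same five-region layout. Changing 10.5.4 alone would create a new conflict with the on-graft definition.
- **12.5.2:** add descriptive within-breast change from Screening to Days 90, 180 and 360, by region, with a per-breast summary if wanted. Give a 95% confidence interval that allows for two breasts in bilateral patients, for example by averaging each patient's breasts before forming the interval or by resampling patients. Show the distribution of filament levels alongside, because the score is ordinal.
- **Reporting:** note that tissue beneath the graft may contribute to the response.

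If Screening testing is not intended, delete the calendar mark and state that the scores do not isolate graft reinnervation.

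The cost is wording in four subsections, plus the definition of a test site. The calendar already schedules the visit and the test. The choice should be made before patients are grafted, because a missed pre-operative score cannot be recovered.

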10.5.5. Response Review

N/A

10.6. Secondary outcome measure: Nipple projection10.6.1. Relevant Subset

All patients (n=15).

10.6.2. Measurement Definition

Nipple projection is defined as the distance from the breast mound to the most projecting tip of the NACgraft, reported in millimeters.

10.6.3. Measurement Methods

Nipple projection is measured with the patient laying down on her back using a depth gauge

10.6.4. Measurement Time Points

Measurements will take place on day 0 (day of surgery), day 42, 3 months, 6 months, and 12 months.

10.6.5. Response Review

N/A

10.7. Secondary outcome measure: Nipple diameter10.7.1. Relevant Subset

All patients (n=15).

10.7.2. Measurement Definition

Nipple diameter is defined as the diameter of the nipple at its base (i.e. where it sits on the breast mound), reported in centimeters.

10.7.3. Measurement Methods

Nipple diameter is measured using a drill gauge.

10.7.4. Measurement Time Points

Measurements will take place on day 0 (day of surgery), day 42, 3 months, 6 months, and 12 months.

10.7.5. Response Review

N/A

10.8. Secondary outcome measure: patient satisfaction

10.8.1. Relevant Subset

All patients (n=15).

10.8.2. Measurement Definition

Patient satisfaction will be measured using a standardized postoperative survey utilizing a LIKERT (numerical) scale to collect feedback from the patient on a variety of indicators including NAC position, overall appearance, symmetry, color, softness, sensation, appearance while nude, appearance when clothed, size, projection, and effect on overall breast appearance. Feedback will additionally be obtained in regard to contribution of reconstructed NAC on sex life, well-being, self-esteem, and whether the patient would undergo the procedure again or recommend the procedure to others. Scores will be reported on a scale of 1 (strongly disagree) to 5 (strongly agree).

A pre-operative survey will collect feedback from the patient on their perceived satisfaction with their reconstructed breast prior to NAC reconstruction. Survey items include satisfaction with breast shape, sensation, sense of well-being, self-esteem, and sex life.

10.8.3. Measurement Methods

Patient satisfaction pre- and post-NAC reconstruction will be measured using standardized Pre-Operative and Post-Operative Nipple Reconstruction Satisfaction Surveys (see Appendix B).

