STATISTICAL CONSIDERATIONS	Time to complete healing for each NAC will be defined as the first weekly visit at which the graft has been deemed to be >99% epithelialized. Max, Mean, Median, and 95% Confidence Interval of these data will be presented, as will percent (%) healed over time for each graft. No formal statistical testing will be performed for any other endpoint; summary statistics will be presented at each time point.

SCHEMA

Inclusion Criteria:

- Patient age 18-65
- Patient desires NAC grafting \geq 3 months after autologous breast reconstruction
- Patient agrees to sleep on back until grafts healed (6 weeks)
- Patient agrees to abstain from aspirin, smoking, alcohol (>2 drinks per day), or excessive caffeine (>300mg per day) until grafts healed (6 weeks)
- Patient agrees to not undergo NAC tattooing until completing study (12 months)
- Patient is able to understand and willing to sign informed consent.

LIST OF ABBREVIATIONS AND DEFINITION OF TERMS

AE	Adverse Event
BD-NRC	Biodesign® Nipple Reconstruction Cylinder
BMSC	Bone Marrow-Derived Mesenchymal Stem Cell
BMI	Body mass index
CGTP	Current Good Tissue Practices
CRF	Case Report Form
CTCAE	Common Terminology Criteria for Adverse Events
Dcl-NHP-NAC	Decellularized Non-Human Primate Nipple-Areolar Complex
DSMC	Data Safety Monitoring Committee
ECOG	Eastern Cooperative Oncology Group
ECM	Extracellular Matrix
FDA	Food and Drug Administration
GCP	Good Clinical Practice
HCT/P	Human Cells, Tissues, and Cellular and Tissue-Based Products
HIPAA	Health Insurance Portability and Accountability Act
HIV	Human Immunodeficiency Virus
IDE	Investigational Device Exemption
IRB	Institutional Review Board
NAC	Nipple-areolar complex
NACgraft™	Decellularized human nipple-areolar complex graft
NHP	Non-Human Primate
N-NAC	Native Nipple-Areolar Complex
PD	Protocol Director
SAE	Serious Adverse Events
SRC	Scientific Review Committee
SWM	Semmes Weinstein Monofilament
VAS	Visual Analog Scale

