10.8.4. Measurement Time Points

The time point will take place at study enrollment (pre-operative survey) and postoperatively at 3 months, 6 months, and 12 months.

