12.6.2. Sample size justification

The proposed sample size of 15 patients is not intended to support definitive conclusions around our primary outcome measures, but rather will (a) provide support that the NAC graft is safe for marketing purposes, (b) will confirm our ability to gather the necessary data in an adequately powered larger clinical study in the future, and (c) provide preliminary estimates of the study measures and their associated variability, in part to better define sample size requirements for the larger study.

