12.6.3. Effect size justification

This is a single arm (non-randomized study) thus effect size is not applicable. Previous literature indicates that NAC reconstruction can be a significant determinant of psychological well-being in breast cancer survivors.^{4,5} In a recent study, 80.3% of women who underwent NAC reconstruction would encourage other women to undergo NAC reconstruction (n=107, no confidence interval given).⁶ Women who have undergone NAC reconstruction have been shown to have significantly higher general (72.2% vs 52.8%, P < 0.0001) and aesthetic (70.5% vs 46.5%, P < 0.0001) satisfaction scores compared to patients without nipple reconstruction (n=490 NAC reconstruction, n=206 without reconstruction).⁷ Furthermore, patients who underwent NAC reconstruction using the Cook Medical BD-NRC (n=82 reconstructions in n=50 patients) only retained 40% nipple projection at 12 months post-reconstruction (3.8 ± 1.5 mm, compared with 10.5 ± 2.2 mm 1 week after surgery).¹² Data from this trial will be compared to these historical figures to look for trends and inform future studies.

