APPENDIX B: Nipple Reconstruction Satisfaction Surveys

Nipple Reconstruction Satisfaction Survey: Pre-operative

You have undergone breast reconstruction after mastectomy and are about to undergo nipple reconstruction with the BioAesthetics NACgraft. The following questions are designed to determine how you are feeling at this time. Please answer each question. Thank you for your feedback.

	Male	Female				
What is your sex?						
	< 18	19 – 35	36 – 50	51 – 65	> 66	
What is your present age?						
	< 3 months	3 – 6 months	6 – 9 months	9 – 12 months	> 12 months	N/A
How long ago was your left breast reconstruction (if applicable)?						
How long ago was your right breast reconstruction (if applicable)?						
				Yes	No	
I agree to sleep on my back for 6 weeks after nipple reconstruction.						
I agree to abstain from aspirin, smoking, excessive alcohol (no more than 2 drinks per day), and excessive caffeine (no more than 300mg per day, or 3 cups of coffee) for 6 weeks after nipple reconstruction.						
I agree to not undergo nipple tattooing for 12 months after nipple reconstruction.						
	Strongly Disagree	Disagree	Neither Agree nor Disagree	Agree	Strongly Agree	N/A
I am satisfied with the shape of my new left breast.						
I am satisfied with the shape of my new right breast.						
I would undergo breast reconstruction again.						
				Yes	No	N/A
My left breast was eligible for a nipple-sparing mastectomy, but I chose to have my nipple removed.						
My right breast was eligible for a nipple-sparing mastectomy, but I chose to have my nipple removed.						

Nipple Reconstruction Satisfaction Survey: Pre-operative

	No Sensation	Low	Normal	High	N/A
What level of pleasant sensation do you have in your left breast?					
What level of pleasant sensation do you have in your right breast?					
What level of unpleasant sensation do you have in your left breast?					
What level of unpleasant sensation do you have in your right breast?					
I had a nipple-sparing mastectomy on my left breast. The sensation in my left nipple is					
I had a nipple-sparing mastectomy on my right breast. The sensation in my right nipple is					
Answer the following items as compared to before your mastectomy.	Much Worse	Worse	About the same	Better	Much Better
My sense of body image is					
My sense of self-esteem is					
My sense of well-being is					
My sex life is					

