Answer the following items as compared to before your breast reconstruction(s).	Much Worse	Worse	About the same	Better	Much Better
My sense of body image is					
My sense of self-esteem is					
My sense of well-being is					
My sex life is					
	Strongly Disagree	Disagree	Neither Agree nor Disagree	Agree	Strongly Agree
Before my mastectomy, my nipples were the same size.					
Before my mastectomy, my nipples were the same color.					
Before my mastectomy, my nipples were symmetrical.					
Nipple reconstruction will complete my breast reconstruction.					
Nipple reconstruction will improve my body image.					
Nipple reconstruction will improve my sense of self-esteem.					
Nipple reconstruction will improve my sense of well-being.					
Nipple reconstruction will improve my sex life.					

Nipple Reconstruction Satisfaction Survey – Post-operative

You have undergone nipple reconstruction with the BioAesthetics NACgraft. The following questions are designed to determine how satisfied you are with the outcome. By checking ONE box in each row below, please indicate how satisfied with your nipple reconstruction operation today. Thank you for your feedback.

Postop Visit: 3 month 6 month 12 month Other _____

	< 18	19 – 35	36 – 50	51 – 65	> 66
What is your present age?					

If you had bilateral nipple reconstruction, please answer the following questions for ONE side only. Then answer the same questions on the following page for the OTHER side.

Breast:  Right  Left	Strongly Disagree	Disagree	Neither Agree nor Disagree	Agree	Strongly Agree
I am pleased to have had nipple reconstruction.					
I am pleased with the position of my reconstructed nipple.					
I am pleased with the overall appearance of my reconstructed nipple.					
I am pleased with the symmetry of my reconstructed nipple.					
I am pleased with the color of my reconstructed nipple.					
I am pleased with the softness of my reconstructed nipple.					
I am pleased with the appearance of my reconstructed nipple when nude.					
I am pleased with the appearance of my reconstructed nipple when clothed.					
I am pleased with the size of my reconstructed nipple.					
I am pleased with the projection (sticking out) of my reconstructed nipple.					
My reconstructed nipple made my new breast look better.					
	No Sensation	Low	Normal	High	
What level of pleasant sensation do you have in your reconstructed nipple?					

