What level of unpleasant sensation do you have in your reconstructed nipple?					

Nipple Reconstruction Satisfaction Survey – Post-operative

If you had bilateral nipple reconstruction, please answer the following questions for the other side.

Breast:  Right  Left	Strongly Disagree	Disagree	Neither Agree nor Disagree	Agree	Strongly Agree
I am pleased to have had nipple reconstruction.					
I am pleased with the position of my reconstructed nipple.					
I am pleased with the overall appearance of my reconstructed nipple.					
I am pleased with the symmetry of my reconstructed nipple.					
I am pleased with the color of my reconstructed nipple.					
I am pleased with the softness of my reconstructed nipple.					
I am pleased with the appearance of my reconstructed nipple when nude.					
I am pleased with the appearance of my reconstructed nipple when clothed.					
I am pleased with the size of my reconstructed nipple.					
I am pleased with the projection (sticking out) of my reconstructed nipple.					
My reconstructed nipple made my new breast look better.					
	No Sensation	Low	Normal	High	
What level of pleasant sensation do you have in your reconstructed nipple?					
What level of unpleasant sensation do you have in your reconstructed nipple?					

Nipple Reconstruction Satisfaction Survey – Post-operative

Please answer the following questions ONCE

Answer the following items as compared to before your mastectomy.	Much Worse	Worse	About the same	Better	Much Better
My sense of body image is					
My sense of self-esteem is					
My sense of well-being is					
My sex life is					
Answer the following items as compared to before your nipple reconstruction(s).	Much Worse	Worse	About the same	Better	Much Better
My sense of body image is					
My sense of self-esteem is					
My sense of well-being is					
My sex life is					
	Strongly Disagree	Disagree	Neither Agree nor Disagree	Agree	Strongly Agree
I am pleased with my body image.					
I am pleased with my sense of well-being.					
I am pleased with my level of self-esteem.					
I am pleased with my sex life.					
I would choose to undergo this type of nipple reconstruction again.					
I would recommend this type of nipple reconstruction to another woman.					
I feel nipple tattooing is necessary in addition to my nipple reconstruction.

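### Four survey items are asked identically before and after surgery, but no within-patient change from the pre-operative answer is planned for them

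*Combined protocol and SAP*

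**What the plan says.** On measurement, Section 10.8.3 states: "Patient satisfaction pre- and post-NAC reconstruction will be measured using standardized Pre-Operative and Post-Operative Nipple Reconstruction Satisfaction Surveys". Section 10.8.4 gives the timing: "The time point will take place at study enrollment (pre-operative survey) and postoperatively at 3 months, 6 months, and 12 months".

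Appendix B shows what can be paired. Both surveys contain a block headed "Answer the following items as compared to before your mastectomy", with the same four items and the same five responses from Much Worse to Much Better. In the post-operative survey this block is answered once per woman, not once per breast. Each survey has a second block on the same four domains, but the reference points differ: before breast reconstruction in the pre-operative survey, before nipple reconstruction in the post-operative one.

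On analysis, the synopsis says of all endpoints other than healing time that "summary statistics will be presented at each time point". Section 12.5.2 lists the maximum, mean, median and a 95% confidence interval for survey scores. Section 12.5.1 adds statistics for subgroups with no missing data or non-adherence. The only comparisons named are external: with the historical figures in Section 12.6.3 and with published survey data in Section 12.7.

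**The concern.** Section 12.1 names body image, self-esteem and psychological well-being among the outcome areas. Section 12.6.3 quotes published figures for general and aesthetic satisfaction, for recommending the procedure and for projection, but none for these four items. The woman's own pre-operative answer is therefore the only quantified reference the plan holds for them, and no section links it to her later answers.

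The second stake is design information. Sections 12.1 and 12.6.2 give as a purpose of the pilot the estimation of measures and their variability, so that a larger study can be sized. If that study uses change on these items, it needs the SD of change, and separate visit summaries do not supply it.

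**Working it through.** **Is there a figure in the plan to reproduce?** No. Section 12.6.2 says "The proposed sample size of 15 patients is not intended to support definitive conclusions around our primary outcome measures" and Section 12.6.3 says "This is a single arm (non-randomized study) thus effect size is not applicable". No SD, correlation or target precision is given, so the numbers below are illustrations.

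**Item match across the two surveys (Appendix B).**

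| Block | Pre-operative reference | Post-operative reference | Matched items |
|---|---|---|---|
| First | before mastectomy | before mastectomy | 4 of 4 |
| Second | before breast reconstruction | before nipple reconstruction | 0 of 4 |

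The first block is a true pre/post pair in wording, reference point and scale. As it is answered once per woman, bilateral grafts create no clustering.

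**Search for a change analysis.** The synopsis and Sections 12.1, 12.3, 12.5.2, 12.6.3 and 12.7 were read for a difference from the pre-operative survey. None plans one.

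**What separate summaries lose.** In women with both surveys, the difference between the two visit means equals the mean change, so that estimate is recoverable. Its SD is not:

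SD(change) = √(SD₁² + SD₂² − 2ρ·SD₁·SD₂), which with equal SDs is SD·√(2(1−ρ)).

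The visit summaries do not contain ρ. They also do not give the median change or the numbers improved, unchanged and worse. For sizing a later study on a fixed mean change, the required number is roughly proportional to the variance of change, 2(1−ρ) in SD² units. That is 1.4 at ρ = 0.3 and 0.6 at ρ = 0.7, so not knowing ρ within this range leaves the size uncertain by a factor of 1.4/0.6 = 2.3.

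**Precision.** Assumptions not in the documents: equal SDs at both visits, the values of ρ, and (for the second column) a loss of 3 women.

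- Paired 95% half-width: t(n−1)·√(2(1−ρ))/√n in SD units. At n = 15, t = 2.145 and 2.145/√15 = 0.554.
- Two visits treated as independent: t(2n−2)·√(2/n). At n = 15, 2.048 × √(2/15) = 0.748.

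| Assumed ρ | 15 pairs | 12 pairs |
|---|---|---|
| 0 | 0.78 SD | 0.90 SD |
| 0.3 | 0.66 SD | 0.75 SD |
| 0.5 | 0.55 SD | 0.64 SD |
| 0.7 | 0.43 SD | 0.49 SD |
| Treated as independent | 0.75 SD | 0.85 SD |

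At 15 pairs, relative to 0.748 SD, the paired interval is about 5% wider at ρ = 0 (0.783/0.748), 12% narrower at 0.3 (0.655/0.748), 26% narrower at 0.5 (0.554/0.748) and 43% narrower at 0.7 (0.429/0.748).

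**The case against.** The strongest reply is that change is already collected. At each post-operative survey a woman rates the same four domains against the time before nipple reconstruction, and percentages better, same and worse can be tabulated from that block. This stands: a reader who inferred that the plan captures no change in these domains would be wrong. But it is a recalled rating, made up to 12 months after surgery, and not the difference between two answers given at the time. The matched items also ask for recall, of life before mastectomy, so neither measure is clean. They are different information and can check each other.

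A reader might also infer that incomplete follow-up will leave each visit summary describing different women. Section 12.5.1 answers this in part, because a complete-data subgroup holds the women constant. It still yields visit summaries rather than differences.

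Nor does Section 12.5.2 itself confine the analysis to separate visits. The per-time-point wording is the synopsis's, and the list of statistics in 12.5.2 is open-ended. A change analysis is not forbidden; it is unspecified.

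Finally, no planned decision depends on this. The survey criterion in Section 12.7 refers to published data, and the change could be computed later from the same records. That limits the weight of the point. Specifying it in advance still avoids choosing items or visits after seeing the data.

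**Conclusion.** The point holds in a limited form: the prospective within-patient change on four identically worded items is not planned, although it would serve the pilot's own aim of estimating variability. It concerns a secondary outcome in a descriptive study of 15 women and does not affect the primary outcomes.

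Two stronger readings are not supported. One is that the paired change would show that the graft altered these domains. There is no control group, and women may enrol as little as 3 months after breast reconstruction (Section 3.1.2), so continuing recovery cannot be separated from any effect of the graft. The other is that pairing brings an assured gain in precision. The gain depends on an unknown correlation and disappears below about 0.09. It is also measured against an independent-visits comparison that the plan does not propose. SD units are moreover a rough metric for single five-level items, so the counts are the more natural summary.

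**What to change.** In Section 12.5.2, for the four items rated against the time before mastectomy, add:

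- the number and percentage of women improved, unchanged and worse from the pre-operative survey to 3, 6 and 12 months;
- the mean or median change at each of these visits with a paired 95% confidence interval, and the SD of change;
- the number of complete pairs behind each figure;
- the recalled-change items alongside, for comparison;
- a statement that the result is uncontrolled, descriptive change and is not attributable to the graft alone.

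State the coding as well, for example Much Worse = 1 to Much Better = 5. Section 10.8.2 defines scores only for the agreement scale, so these items have no stated numeric values.

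The cost is a few lines of text and 4 × 3 = 12 descriptive intervals. No new visit, question or patient is needed.
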